#### Notes:

- AEs coded using MedDRA version will be noted in the footnote of the tables and listings.
- CTCAE

### 5.7.2 Laboratory Evaluations

Laboratory values will be graded by NCI CTCAE version 4.03 (or higher), if no grading exists values will be classified into low/normal/high based on laboratory normal ranges. Each parameter will be presented by descriptive statistics at each visit including change from baseline (screening). Shift tables for CTCAE grades and normal ranges will be presented.

All values should be reported in SI units (if applicable), results reported in non-SI unit should be converted to SI unit. Missing values will be excluded.

Only patients with non-missing change from baseline data at the visit will be included in the post-baseline summary statistics at the visit. Baseline is defined as the last measurement prior to dosing.

Results from the following laboratory parameters will be summarized by cohort and time point:

**Haematology:** Haemoglobin, haematocrit, erythrocytes (RBC), reticulocyte count, platelets, leukocytes (WBC), differentials (counts): neutrophils, eosinophils, lymphocytes, monocytes, basophils.

**Coagulation:** Prothrombin time expressed as International normalized ratio (INR), activated partial thromboplastin time (aPTT).

**Biochemistry:** Total protein, albumin, alkaline phosphatase, total bilirubin, calcium, cholesterol, chloride, creatine kinase, aspartate aminotransferase (AST), alanine aminotransferase (ALT), lactate dehydrogenase, C-reactive protein (CRP), lipase, pancreatic amylase, glucose, inorganic phosphorus, magnesium, potassium, sodium, triglycerides, urea/blood urea nitrogen, uric acid, creatinine (creatinine clearance estimated according to the Cockcroft-Gault formula).

Aspartate aminotransferase (AST), alanine aminotransferase (ALT), total and conjugated bilirubin, albumin, alkaline phosphatase (ALP), gamma-glutamyl-transferase (GGT), amylase, bicarbonate, calcium, chloride, total cholesterol, creatine phosphokinase (CPK), C-reactive protein (CRP), creatinine, blood urea nitrogen (BUN), glucose, phosphate, lactate dehydrogenase (LDH), lipase, magnesium, potassium, total protein, sodium, triglycerides, urate.

**Urine from dipstick:** Protein, glucose, ketones, red (RBC) and white blood cells (WBC), pH, specific gravity.

**Detailed Urinalysis** (if clinically significant positive results from the dipstick): bacteria, casts (RBC, haemoglobin, hyaline, WBC), RBC, WBC, mucus, oxalates, epithelial cells, renal and squamous epithelial cells, uric acid crystals, unspecified crystals, urate, yeast.

**Cardiac markers:** Serum troponin, N-terminal pro-peptide BNP

Laboratory parameters other than cardiac markers are assessed at following time points:

- At screening
- During Cycle 1 on Day 1, Day 3 (only Part A), Day 8, Day 15 and Day 22
- During other Cycles on Day 1 and Day 15
- At EOT visit

Cardiac serum markers are to be collected:

- At baseline
- During Cycle 1: on Day 22
- During other Cycles on Day 1 and Day 15
- At EOT visit

Absolute values and changes values from baseline for haematology, biochemistry and coagulation assessments will be summarized (cf. notes in section 4.1).

Shift tables for Out of Normal Range Results for haematology, biochemistry and coagulation assessments will be summarized.

Shift tables for CTCAE grades for haematology, biochemistry and coagulation assessments will be summarized.

Local dipstick urinalysis ( ) as well as results will be summarized according to being normal or abnormal.

All laboratory results will be listed.

A separate listing for abnormal lab values (Grade 3 and higher, and low/high values) will be presented.

**Notes:**

- All results outside ranges will be flagged in the data listings as follows:
  - Out-of-reference-range values will be marked as high (H) or low (L).
  - Values falling outside the clinically significant reference range of the respective laboratory will be marked as clinically significant laboratory abnormalities (i.e., potentially clinically relevant) and labelled in addition by “CS”. Marked laboratory abnormalities will be labeled in the subject listings as “HH” for significantly high or “LL” for significantly low.
- Repeat laboratory results within a visit will replace the original value.
- Unscheduled results will be listed only.

Any other laboratory results will be listed only.

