#### **7.4.6.1.1 Haematologic Toxicities for Solid Tumour Patients**

If  $\geq$  CTCAE grade 3 neutropenia or  $\geq$  CTCAE grade 3 thrombocytopenia have been demonstrated, testing for these parameters must be repeated at least twice a week until resolution to  $\leq$  CTCAE grade 1 neutropenia or  $\leq$  CTCAE grade 1 thrombocytopenia, to allow for re-treatment and then at least weekly until either resolution or until stabilisation.

**Table 4** Dose modifications for haematologic toxicities

Dose Modifications for CB-103	
Worst Toxicity CTCAE Grade unless otherwise specified (Value)	At any time during a cycle of CB-103 (including intended day of dosing)
Haematologic toxicities:	
Neutropenia (ANC)	
Grade 1 (ANC < LLN - 1.5 x 10  /L) & Grade 2 (ANC < 1.5 - 1.0 x 10  /L)	Maintain dose level
Grade 3 (ANC < 1.0 - 0.5 x 10  /L)	Omit dose administration until resolved to ≤ grade 1, 
 
• If resolved in ≤ 7 days, then maintain dose level
 
• If resolved in > 7 days, then ↓ 1 dose level
 

Grade 4 (ANC < 0.5 x 10  /L)	Omit dose administration until resolved to ≤ grade 1, then ↓ 1 dose level
Grade 3 Febrile neutropenia (ANC < 1.0 x 10  /L with a single temperature of >38.3°C or a sustained temperature of ≥38°C for more than one hour)	Omit dose administration until resolved, then ↓ 1 dose level
Thrombocytopenia	
Grade 1 (PLT < LLN - 75 x 10  /L)	Maintain dose level
Grade 2 (PLT < 75 - 50 x 10  /L) & Grade 3 (PLT < 50-25 x 10  /L)	Omit administration dose until resolved to ≤ grade 1, then: 
 
• If resolved in ≤ 7 days, then maintain dose level
 
• If resolved in > 7 days, then ↓ 1 dose level
 

Grade 4 (PLT < 25 x 10  /L)	Omit administration dose until resolved, then ↓ 1 dose level

 Common Terminology Criteria for Adverse Events (CTCAE Version 4.03)

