**Phase I, Part A - MTD/RP2D confirmatory cohort and Phase IIA, Part B – Expansion:**

**For patients with solid tumours who are not hospitalized:**

- Patients will undergo daily visits for 3 days and will get their CB-103 doses administered in the hospital. Patients will stay for at least 3 hours following each administration of CB-103 to allow safety reporting with the exception of the first day where the patients should stay for up to 8 hours post-dose.

In case CB-103 is given BID, one more overnight hospital stays at Day 8 in cycle 1 may be necessary to allow late samples collection.

- Weekly visits to monitor safety and perform ECG monitoring and PK sampling are planned during the rest of the treatment period for the 1st cycle of CB-103 (28 days).
- Every 2 weeks visits to monitor safety and perform PK sampling are planned from cycle 2 until the completion of cycle 6.
- After cycle 6, subsequent visits are planned every 4 weeks if no medical issue or complication occurred in the previous cycles.
- End-of-Treatment (EOT) visit within 14 days after the last dose of CB-103 (within the 12 cycles period).
- Safety follow-up visit (End-of-Study) for each patient within 28 days after the last dose of CB-103.
- Survival follow-up (e.g. per telephone) for 1 year is planned every three months after the End-of-Study or after the last treatment cycle (if outside of the 12 cycles period), and every six months thereafter for the 2nd year.
- Further visits might be considered, depending on the health status of the patient, as determined by the treating Investigator of the respective investigational site.
- More frequent laboratory safety tests (e.g., to closely monitor the liver function), are possible and can be performed outside the study site for those patients living far away, if necessary. The laboratory reference ranges from the local laboratories must be collected and filed in the laboratory report together with the patients' medical records. Care should be taken that any outliers possibly produced by the local laboratory findings are investigated at the study site.

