### **8.2.1 Adverse Events**

An adverse event for the purposes of this protocol is the appearance of (or worsening of any pre-existing) undesirable sign(s), symptom(s), or medical condition(s) occurring after signing the informed consent even if the event is not considered to be related to the study drug(s). Please refer to Section 7.1 to Section 7.4 for the protocol-specific definitions of study drug and study treatment.

Adverse events will be assessed according to CTCAE version 4.03. If CTCAE grading does not exist for an adverse event, the severity of mild, moderate, severe, life threatening and death, or grades 1 - 5, will be used. Adverse event monitoring should be continued for at least 4 weeks following the last dose of study treatment.

Adverse events (but not serious adverse events) occurring before starting study treatment but after signing the ICF are recorded on the Medical History/Current Medical Conditions eCRF. Abnormal laboratory values or test results constitute adverse events only if they induce clinical signs or symptoms, are considered clinically significant or require therapy (e.g., any haematologic abnormality that requires transfusion or cytokine treatment); and should be recorded on the Adverse Events eCRF under the signs, symptoms or diagnosis associated with them. In addition, isolated abnormal laboratory values that are considered clinically significant (e.g., cause study discontinuation or constitutes in and of itself a Serious Adverse Event) should be recorded on the Adverse Events eCRF. Serious adverse events occurring after signing the ICF are recorded on the Adverse Event eCRF.

The occurrence of adverse events should be sought by non-directive questioning of the patient at each visit during the study. Adverse events also may be detected when they are volunteered by the patient during or between visits or through physical examination, laboratory test, or other assessments. As far as possible, each adverse event should be evaluated to determine:

1. The severity grade (CTCAE grade 1-5)
2. Its relationship to the study drug (suspected/not suspected)
3. Its duration (start and end dates or if continuing at final exam)
4. Action taken (no action taken; study drug dosage adjusted/temporarily interrupted; study drug permanently discontinued due to this adverse event; concomitant medication taken; non-drug therapy given; hospitalisation/prolonged hospitalisation)

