## 8.2.4 Laboratory Safety Assessments

Laboratory safety tests shall be performed at time-points specified in the Schedule of Assessments ([Appendix 1](#) and [Appendix 2](#)).

Additional blood or urine samples may be taken at the discretion of the Investigator if the results of any test fall outside the reference ranges, or clinical symptoms necessitate additional testing to monitor patient's safety. Where the clinical significance of abnormal

lab results is considered uncertain, screening lab tests may be repeated before enrolment to confirm eligibility.

In the event of unexplained abnormal clinically significant laboratory test values, the tests should be repeated immediately and followed up until they have returned to the normal range and/or an adequate explanation of the abnormality is found. Results of clinical laboratory testing will be recorded on the eCRF.

Samples for the following blood and urine laboratory tests will be collected as specified in the Schedule of Assessments ([Appendix 1](#) and [Appendix 2](#)) and sent to the local laboratory for analysis.

- **Haematology:** Haemoglobin, haematocrit, erythrocytes (RBC), reticulocyte count, platelets, leukocytes (WBC), differentials (counts): neutrophils, eosinophils, lymphocytes, monocytes, basophils.
- **Coagulation:** prothrombin time (expressed as INR) and activated partial thromboplastin time (aPTT).
- **Blood chemistry:** AST, ALT, total and conjugated bilirubin, ALP, gamma-glutamyl-transferase ( $\gamma$ -GT), creatine phosphokinase (CPK), albumin, creatinine, urea nitrogen, total protein, sodium, chloride, calcium, bicarbonate, phosphate, potassium, triglycerides, total cholesterol, glucose, C-reactive protein (CRP), lipase, urate and lactate dehydrogenase.
- **Serology:** human immunodeficiency virus (HIV), hepatitis B (HBV) or C (HCV).
- **Pregnancy test:** All women of childbearing potential (including those who have had a tubal ligation) will have serum or urine pregnancy tests at the time-points specified in the Schedule of Assessments ([Appendix 1](#) and [Appendix 2](#)). Pregnancy tests will also be done whenever one menstrual cycle is missed during the active treatment period (or when potential pregnancy is otherwise suspected) to confirm the patient has not become pregnant during the study.

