#### **4.1.4 Visit Windows**

All data will be analyzed using nominal study visit as defined in the Study Schedule and eCRF. No visit windows will be applied for summary and analysis.

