#### Notes:

- Any duration [days] = end date – onset date + 1
- All data will be listed
- All unscheduled visits will be summarized into one visit as the final visit in summary tables. In case of multiple unscheduled assessments, the first one will be considered in the summary table but will all be listed.

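### SAP 5.7.2 lets any within-visit repeat overwrite a laboratory value and only lists unscheduled results, in conflict with SAP 5.1, and no rule brings the worst post-baseline value into the shift tables (minor)

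*SAP*

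**What the plan says.** The notes to SAP 5.7.2 (Laboratory Evaluations) hold two rules. For repeats: "Repeat laboratory results within a visit will replace the original value". For unscheduled samples: "Unscheduled results will be listed only". The repeat rule is not limited to samples that were haemolysed, mislabelled or otherwise invalid.

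The general notes in SAP 5.1 treat unscheduled data differently. They pool unscheduled visits into one final visit in the summary tables and add: "In case of multiple unscheduled assessments, the first one will be considered in the summary table but will all be listed". SAP 4.1.4 assigns data by nominal visit: "No visit windows will be applied for summary and analysis".

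SAP 5.7.2 and protocol 10.6.1.2 plan shift tables for CTCAE grades and for normal ranges. Neither says which post-baseline value feeds them. SAP 5.7.2 also plans a listing of all results and a separate listing of grade 3 or higher and low/high values.

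The protocol generates repeats and extra samples in several ways:

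- Section 8.2.4, for unexplained, clinically significant abnormal values: "the tests should be repeated immediately and followed up until they have returned to the normal range". The same section allows further samples at the investigator's discretion when a result is out of range.
- Section 7.4.6.1.1, after grade 3 or higher neutropenia or thrombocytopenia: "testing for these parameters must be repeated at least twice a week until resolution". Sections 7.4.6.1.2 and 7.4.6.1.3 have similar rules for renal and hepatic values.
- Section 8.1: "More frequent laboratory safety tests (e.g., to closely monitor the liver function), are possible and can be performed outside the study site".

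**The concern.** Repeats and extra samples are not taken at random. They tend to follow an abnormal result, so a rule that overwrites originals or leaves out unscheduled values acts where extreme values are most likely. A shift table is normally read as showing how far each patient's laboratory grade moved from baseline. If the extreme value has been overwritten or left out, the table shows a milder shift than was observed.

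Safety laboratory data are part of the primary endpoint of the Part A confirmatory cohort (SAP 2.5), and SAP 5.7 calls safety the primary analysis. The plan protects the worst observation elsewhere: SAP 5.7.1 gives precedence to the most severe rating of an adverse event, and protocol 10.6.1.4 summarises the worst ECG change. It has no matching rule for laboratory data. In addition, because 5.1 and 5.7.2 differ without a stated precedence, two programmers could build different tables from the same data.

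**Working it through.** No design figure is involved and the plan states none on this point, so the check sets the rules side by side.

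**Direction.** For one patient, one parameter and one direction of abnormality, let R be all recorded post-baseline values and S the values that the rules allow into the table. S is a subset of R, so worst(S) cannot exceed worst(R). Equality holds only if the rules happen to retain the worst value.

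**Each route by which an extreme value can arise:**

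| Where the extreme value occurs | Rule | In the shift table? |
|---|---|---|
| Scheduled sample, no repeat | none needed | Yes |
| Scheduled sample, milder repeat in the same visit | 5.7.2, repeat replaces | No |
| Scheduled sample, worse repeat in the same visit | 5.7.2, repeat replaces | The repeat is used; the visit's grade rises, but not above the worst recorded |
| Unscheduled sample | 5.7.2, listed only | No |
| Unscheduled sample | 5.1, first one used | Only if it was the first unscheduled assessment |

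Settling the conflict between 5.1 and 5.7.2 in either direction still leaves routes by which the worst value drops out.

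**Is 5.7.2 meant as an exception to 5.1?** Perhaps. The laboratory time points in SAP 5.7.2 omit unscheduled visits, whereas the lists for vital signs (5.7.3), ECG (5.7.4) and physical examination (5.7.5) include them. Yet SAP Appendix 3 marks chemistry, haematology and coagulation at unscheduled visits. The precedence has to be inferred.

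**What catches the value elsewhere.**

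1. Listings: all results, plus the grade 3 or higher listing (SAP 5.7.2).
2. Adverse events. Protocol 8.2.1: "Abnormal laboratory values or test results constitute adverse events only if they induce clinical signs or symptoms, are considered clinically significant or require therapy". Protocol 9.3.5.5 adds values that lead to a change in study treatment. The immediate repeats required by 8.2.4 concern clinically significant values, which therefore qualify. The renal, hepatic and blood-count levels that trigger twice-weekly retesting generally also require dosing to be held (Tables 4 to 6), so they qualify as well. SAP 5.7.1 tabulates adverse events at the most severe rating.
3. DLTs: SAP 5.7.1 gives them their own summary table and listing.
4. Dose decisions: the BLRM uses DLT counts in the dose-determining set, and the Cohort Review Committee reviews clinically significant laboratory abnormalities directly (protocol 10.8.1). Neither uses the shift tables.

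**What is left.** The exposed value is extreme, is reported neither as an adverse event nor as a DLT, and is either repeated at discretion within a visit or seen only at an unscheduled visit. The protocol expects that such values can exist: its exceptions to the DLT criteria cover grade 3 or higher investigations judged not clinically significant.

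**The case against.** The best defence has four parts.

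- **A specific section normally overrides a general one.** On that reading 5.7.2 governs laboratory data and there is no conflict. This is a fair convention, but it is not written down, and it settles on the rule that excludes every unscheduled value.
- **SAP 5.7.2 summarises laboratory results by cohort and time point.** Shift tables may therefore be by visit, needing one value per visit, with a worst-on-study display as an extra. Notable vital signs in 5.7.3 are handled by visit too. Even so, a valid original is overwritten within its own visit. The table shells mentioned in SAP 5.1 are not available and might define the shift tables, though 5.1 refers to them only for percentage denominators.
- **Follow-up testing starts after the toxicity has been shown.** If the index value came from a scheduled visit and was not overwritten, it is in the table, and later listed-only values matter only if they are worse. This stands and narrows the effect.
- **The adverse event and DLT tables catch most values that matter.** This also stands.

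A reader might infer more than the documents support:

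- *That the shift tables are the only planned table grading a value judged not clinically significant.* Protocol 2.5.6 reports a grade 3 gamma-glutamyl transferase elevation that was asymptomatic and judged not clinically significant, yet was recorded as a DLT, and DLTs have their own table.
- *That extra tests can never be tied to a scheduled visit, because no visit windows apply.* The schedules of assessments allow laboratory samples within 24 hours either side, so some extra tests can serve as the scheduled sample.
- *That the share of parameters without a mandated dose action measures the problem.* Such a count mixes parameters with and without a CTCAE grade, ignores the adverse event criteria that apply to every parameter, and says nothing about patients or events.

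**Conclusion.** The point holds as a minor defect in a stated analysis rule. The CTCAE and normal-range shift tables can equal or understate the worst recorded post-baseline abnormality and cannot overstate it. The direction is certain. The size cannot be derived, because the documents give no frequency of repeats or unscheduled samples and define no laboratory grade 3 or higher rate.

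No data are lost, and the text does not support an inference that dose escalation or safety oversight is compromised. What is affected is the accuracy of a summary display that forms part of the confirmatory cohort's primary safety evaluation. The conclusion assumes that the notes in 5.7.2 apply to the shift tables as well as to the by-visit statistics, and that the unseen table shells add no worst-value rule.

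**What to change.** In SAP 5.7.2, replace the two notes on repeat and unscheduled results with text to this effect:

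- The original value is kept unless it is documented as technically invalid.
- CTCAE and normal-range shift tables use the worst value per patient and parameter, with high and low directions handled separately where both apply. All scheduled, repeat and unscheduled samples after first dose and up to 28 days after last dose are eligible.
- By-visit statistics use the scheduled value (the first valid one).
- Baseline remains as defined in SAP 4.1.2.
- For laboratory data, this section takes precedence over the unscheduled-visit note in 5.1.

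The 28-day limit matches the adverse event reporting period in protocol 9.3.1 (4 weeks × 7 days = 28 days). A limit of on-treatment samples alone would lose end-of-treatment samples taken after the last dose, because SAP 4.1.3 closes the Treatment Period at that dose. The baseline line is needed because protocol 8.2.4 allows screening tests to be repeated, and 4.1.2 already takes the last non-missing pre-dose value.

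The cost is SAP wording and minor programming, since the values are already collected. The shift tables may look slightly less favourable.

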### 5.7.3 Vital Signs

Absolute as well as change from baseline results for systolic and diastolic blood pressure, pulse rate, Body Mass Index (BMI), weight and oral temperature will be summarized by cohort and visit, using standard descriptive statistics. All vital signs will be listed together with flags for outside of reference range.

Only patients with non-missing change from baseline data at the visit will be included in the post-baseline summary statistics at the visit.

Frequency of patients with notably abnormal vital signs will be provided by cohort and visit and will be defined as follows:

- Systolic blood pressure [mmHg]:  $\geq 180$  mmHg or  $\leq 90$  mmHg with increase or decrease from baseline of  $\geq 20$  mmHg

- Diastolic blood pressure [mmHg]:  $\geq 105$  mmHg or  $\leq 50$  mmHg with increase or decrease from baseline of  $\geq 15$  mmHg

- Pulse rate [bpm]:  $\geq 120$  bpm or  $\leq 50$  bpm with increase or decrease from baseline of  $\geq 15$  bpm

Baseline is defined as the last measurement prior to dosing.

Systolic and diastolic blood pressure as well as pulse rate is recorded at following time points:

- At screening
- During Cycle 1: on Days 1, 2 (only **Part A**), 3 (only **Part A**), 8, 15 and 22
- During other Cycles on Day 1 and Day 15
- At EOT visit
- At unscheduled visits.

Oral temperature is taken at following time points:

- At baseline
- During Cycle 1: on Days 2 (only **Part A**), 3 (only **Part A**), 8, 15 and 22
- During other Cycles on Day 1
- At EOT visit
- At unscheduled visits.

Weight, and hence BMI, is assessed at following time points:

- At baseline
- During all Cycles other than 1: on Day 1
- At EOT visit
- At EOS visit
- At unscheduled visits.

Note:

- All results outside ranges will be flagged in the data listings as follows:
  - Out-of-reference-range values will be flagged as high (H) or low (L) where reference ranges are as follows:
    - Weight:  $\geq 7\%$  increase or decrease from baseline weight
    - Systolic blood pressure [mmHg]:  $\geq 180$  mmHg/ $\leq 90$  mmHg with increase/decrease from baseline of  $\geq 20$  mmHg
    - Diastolic blood pressure [mmHg]:  $\geq 105$  mmHg/ $\leq 50$  mmHg with increase / decrease from baseline of  $\geq 15$  mmHg
    - Pulse rate [bpm]:  $\geq 120$ bpm/ $\leq 50$  bpm with increase / decrease from baseline of  $\geq 15$  bpm
  - Values falling outside the clinically significant reference range of the respective laboratory will be marked as clinically significant vital signs abnormalities (i.e., potentially clinically relevant). Marked abnormalities will be labelled in the subject listings as “HH” for significantly high or “LL” for significantly low.

